7.2.2 Adjunctive Procedures

Adjunctive procedures during the index procedure, as part of SOC is allowed. All adjunctive procedures will be documented on the appropriate eCRF.

7.3 Post-Index Procedure and Discharge

Medication therapy and medical treatment will be conducted at the discretion of the PI per the investigational site's SOC. Participants will be treated and discharged according to the site's SOC. Prior to discharge, the following data will be collected and documented on the appropriate eCRF for participants into whom the Pristine™ Catheter was placed:

- Documentation of Adverse Events (AEs): Documentation of AEs (refer to Section 9) that have occurred since the start of the index procedure (defined to begin at the time of the initial skin puncture to gain vessel access).
- Documentation of Re-Interventions: Any additional interventions the participant has undergone since the completion of the index procedure (defined to end at the time of leaving the operating room).

7.4 Participant Follow-Up

7.4.1 Follow-Up Intervals and Methods

Enrolled participants will have follow-up visits at 1-month, 3 months, 6-months, and 12-months via either in person visit or telephone call. For participants into whom the Pristine™ Catheter was introduced during the index procedure, but procedure success was not achieved, only the procedure eCRF will be collected and limited to the collection of safety events and interventions for up to 30 days.

Follow-up windows will be calculated from the index procedure date. Refer to Section 1.2 for an overview of follow-up window time frames and requirements for each visit. The

following data will be collected and documented on the appropriate eCRF for each follow-up unless otherwise specified for treated participants:

- Hemodialysis Catheter Assessment:
 - Document how the participant has been receiving hemodialysis and document the date of the participant's last HD session.
- Dialysis Session Blood Flow Rate:
 - If dialyzing through the Pristine™ Catheter, document the reported dialysis sessions and details such as date of dialysis session, average blood flow rate, number of line reversals, and length of dialysis session.
- If Needed:
 - Documentation of any protocol deviations that have occurred since the last follow-up.
 - Documentation of occurrence and / or status of AEs since the last follow up (refer to Section 9).
 - Any catheter reinterventions the participant has undergone since the prior follow-up.

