3.2 Secondary Endpoints

The following secondary endpoints will be evaluated using descriptive statistics to provide further information related to the safety and performance of the Pristine™ Long-Term Hemodialysis Catheter. All secondary endpoints will be summarized with descriptive statistics.

- *Rate of freedom from catheter-related bloodstream infection (CRBSI)*, defined by 2019 KDOQI Guidelines for CRBSI through 1-month, 3-months, 6-months, and 12 months post-index procedure.

- *Rate of freedom from Device and/or Procedure-related adverse events*, at 1-month, 3-months, 6-months, and 12 months post-index procedure.
- *Rate of Technical Success*, defined as the successful placement of the Pristine™ Long-Term Hemodialysis Catheter, as assessed by the Investigator during the Index Procedure.
- *Overall Participant Survival Rate* at 1-month, 3-months, 6-months, and 12 months post-index procedure, defined as the proportion of participants that have not died from any catheter related complication.
- *Overall Catheter Survival Rate* at 1-month, 3-months, 6-months, and 12 months post-index procedure, defined as the proportion of Pristine™ Catheters that have not been removed for any cause.
- *Overall Patency Rate*, at 1-month, 3-month, 6-months, and 12-months post-index procedure, defined as the Pristine™ catheter having the ability to achieve a mean dialysis blood flow of $\geq 300\text{mL/min}$ without need for additional interventions.^{5,6}

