7.5 Participant Investigation Completion and Premature Discontinuation

Following the index procedure, every participant into whom the Pristine™ Catheter was placed should remain in the study until completion of the required follow-up period or until day of remove of the Pristine™ Catheter. The follow-up period for this clinical investigation is 12 months (365 ± 30 days) for participants who had the Pristine™ Catheter successfully placed. An enrolled participant is considered to have completed the study if the participant has completed the formal follow-up period associated with this clinical investigation through the 12-Month follow-up as described in the Schedule of Activities (Section 1.3).

Upon investigation completion or premature discontinuation (in the situations where applicable), the participant's continued care should be administered per SOC at the discretion of the PI and / or their primary care physician.

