10.5 Primary Endpoint

The combined primary endpoint is the overall rate of infectious complications and non-infectious complications requiring revision to maintain patency and improve access performance at 3 months. Based on the DOPPS study data, competitor control devices had an average incidence rate of 31.5 complications per 1000 patient days. To show non-inferiority of the Pristine™ Catheter, a 5 complications per 1000 patient days non-inferiority margin is used to establish a performance goal (PG) of 36.5 events per 1000 patient days.

The analysis of the primary endpoint will be based on the following test of Poisson rate:

H₀: The complication rate through 3 month is greater than or equal to 36.5 events per 1000 patients days at 3 months.

H₁: The complication rate through 3 month is less than 36.5 events per 1000 patient days at 3 months.

That is:

$$\mathbf{H_0: \lambda \geq \lambda_0}$$

$$\mathbf{H_1: \lambda < \lambda_0}$$

Where λ_0 is the PG of 36.5 events per 1000 patient days.

A one-sided p-value will be derived based on an Poisson distribution. The Pristine™ Catheter will be considered to have achieved the primary endpoint objective if the one-sided p-value is less than 0.025.

Conditioned on the success of the above test, a superiority test will be conducted to show that the Pristine™ Catheter is superior to the performance goal. The above test will be repeated with a PG of 31.5 events per 1000 patient days.

The analyses of the primary endpoint will be based on the ITT population and repeated with per-protocol population as sensitivity analyses.

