Possibly Related AE	An AE is possibly related if it is capable of being related but relatively unlikely or there is insufficient information to determine if the AE is related to the device or procedure.
Post Procedure Event	AE that occurred after the index procedure.
Principal Investigator	Qualified person responsible for conducting the clinical investigation at an investigation site. If a clinical investigation is conducted by a team of individuals at an investigation site, the PI is responsible for leading the team.
Procedure access Site	A site of incision access during index procedure.
Procedural Event	AE that occurred during the index procedure.
Procedure Duration	The duration of the index procedure as defined in this CIP.
Procedure Related AE	AEs directly attributable to the index procedure.
Procedure Success	Successful catheter creation using the Pristine™ Long-Term Hemodialysis Catheter with flow confirmed through the catheter.
Recruitment	Active efforts to identify participants who can be suitable for enrolment into the clinical investigation.
Re-interventions	Any additional procedures with the initial catheter after the index procedure.
Screen Failure	A participant who is excluded from this clinical investigation as based on the eligibility criteria.
Serious Adverse Device Effect (SADE)	ADE that has resulted in any of the consequences characteristic of a SAE.

Term	Definition
Serious Adverse Event	
An AE that led to any of the following:
 
 • Death; or • Serious deterioration in the health of the participant, users or other persons as defined by one or more of the following: 
 - A life-threatening illness or injury; or - A permanent impairment of a body structure or a body function including chronic diseases; or - In-patient or prolonged existing hospitalization; or - Medical or surgical intervention to prevent life-threatening illness or injury or permanent impairment to a body structure or a body function; or • Fetal distress, fetal death or a congenital abnormality or birth defect including physical or mental impairment. 
Note: Planned hospital visits and / or hospital stays, or procedures required by this CIP (including subsequent interventions assessed in the clinical investigation endpoints), without serious deterioration in health should not be considered SAEs.

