Serious Health Threat	Signal from any AE or device deficiency that indicates an imminent risk of death or a serious deterioration in the health in participants, users, or other persons, and that requires prompt remedial action for other participants, users, or other persons. This would include events that are of significant and unexpected nature such that they become alarming as a potential serious health hazard or possibility of multiple deaths occurring at short intervals.
Severe AE	Symptom(s) causing severe discomfort to the participant and / or significant impact on the participant's usual activity. Additional intervention and / or treatment is necessary. Additional sequelae occur.
Severity (of AE)	The intensity of the AE as experienced by the participant or user.
Significant Deviation	A deviation that occurs to protect the life or physical well-being of a participant in an emergency, or a deviation that may affect the

Term	Definition
	scientific soundness of the clinical investigation, or a deviation pertaining to the rights, safety or welfare of human participants.
Source Data	All information in original records, certified copies of original records of clinical findings, observations, or other activities in a clinical investigation, necessary for the reconstruction and evaluation of the clinical investigation. This includes electronic source data initially recorded in an electronic format.
Source Document	Original or certified copy of printed, optical, or electronic document containing source data.
Sub-Investigator	Individual member of the investigation site team designated and supervised by the PI at an investigation site to perform clinical investigation-related procedures or to make important clinical investigation-related and medical treatment decisions.
Thrombosis	The formation or presence of a blood clot resulting in catheter occlusion.
Treated Participant	Defined as a participant that has met all eligibility criteria, into whom the Pristine™ Long-Term Hemodialysis Catheter was introduced and in whom procedure success was achieved.

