### **5.3.2 Rate of freedom from Device and/or Procedure-related adverse events, at 1-month, 3-months, 6-months, and 12-months post-index procedure.**

#### **Binary Analysis**

Subject will be considered as having device and/or procedure-related adverse events for a given visit if the subject has experienced device and/or procedure-related adverse events prior to the upper limit of visit window for the visit:

- **AE CRF Page:** AE start date <= upper limit of the visit window AND (Relationship to Device: Is 'Related' or 'Likely Related' OR Relationship to Procedure: Is 'Related' or 'Likely Related') ; subject will be considered as a failure at the AE date

If the subject has not become failure and experience one of the following events prior to the lower limit of visit window, then subject will be considered as non-evaluable at the earliest occurrence of following event dates.

- Catheter has been removed due to Kidney Transplant, Transferred to AVG/AVF, Peritoneal Dialysis, Withdrawal of Care, or Other reasons
  - **Hemodialysis Catheter Re-Interventions CRF page:** *Catheter removal Equals Yes AND Reason for catheter removal Equals: Kidney Transplant, Transferred to AVG/AVF, Peritoneal Dialysis, Withdrawal of Care, or Other*

OR

- Subject has discontinued from the study.

If the subject has experienced any of the above non-evaluable events prior to the lower limit of visit window subject will be counted as a non-evaluable for a given visit. Else subject will be considered as a success (freedom from device and/or procedure-related adverse events) for a given visit.

The rate of freedom from device and/or procedure-related adverse events will be reported with 95% confidence interval from the exact binomial method. The analysis will be performed on the ITT population through 1-month, and mITT population through 1-month, 3-months, 6-months, and 12-months.

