### **5.3.3 Rate of Technical Success, defined as the successful placement of the Pristine™ Long-Term Hemodialysis Catheter, as assessed by the Investigator during the Index Procedure.**

Subject will be considered as having technical success if the subject has experienced successful placement of the catheter at the intended site during the procedure:

- **Procedure Overview Part-1 CRF Page:** Was there successful placement at the intended site of the Pristine™ Long-Term Hemodialysis Catheter: Equals Yes

The rate of technical success will be reported with 95% confidence interval from the exact binomial method. The analysis will be performed on the ITT population.

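### A catheter placed without confirmed flow can be a Technical Success while Protocol 7.4.1 limits its data to 30 days, in conflict with Protocol 7.5 and the protocol's own ITT population

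*Protocol*

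**What the plan says.** Two definitions of success are in use.

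- **Technical Success** (Protocol 3.2) is "defined as the successful placement of the Pristine™ Long-Term Hemodialysis Catheter, as assessed by the Investigator during the Index Procedure". SAP 5.3.3 scores it from one CRF item, "Was there successful placement at the intended site of the Pristine™ Long-Term Hemodialysis Catheter: Equals Yes", on the SAP's ITT population. Neither mentions flow.
- **Procedure Success** (Protocol Appendix A) is "Successful catheter creation using the Pristine™ Long-Term Hemodialysis Catheter with flow confirmed through the catheter". Appendix A also builds it into the Treated Participant, into whom the catheter "was introduced and in whom procedure success was achieved".

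Protocol 7.4.1 makes follow-up depend on Procedure Success. For a participant into whom the catheter was introduced without it, "only the procedure eCRF will be collected and limited to the collection of safety events and interventions for up to 30 days". Protocol 7.5 says something different: "every participant into whom the Pristine™ Catheter was placed should remain in the study until completion of the required follow-up period", or until the catheter is removed.

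Protocol 10.3 defines the ITT as eligible, consented participants in whom the catheter was placed, with no condition on flow or dialysis. Protocol 10.5 states: "The analyses of the primary endpoint will be based on the ITT population". Protocol 10.6 uses the same population for the secondary endpoints.

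The SAP (4.1) widens the ITT to everyone whose procedure was initiated and adds an mITT of those treated with the study device. Participants with the device inserted but no first dialysis session are in the SAP's ITT and not in its mITT. The primary endpoint, catheter survival and patency are analysed on the mITT (SAP 5.2.2, 5.3.5, 5.3.6). Freedom from device- or procedure-related AEs (SAP 5.3.2) is also run on the wider set: "The analysis will be performed on the ITT population through 1-month".

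**The concern.** A catheter that is in position but through which flow is not confirmed is an early performance failure. The plan allows it to be scored as a success on the placement endpoint. Because the other definition was not met, the plan then reduces the data collected on it. Protocol 3 says the results are intended for the device's labeling, so a reader of the Technical Success rate would want to know whether it includes catheters without flow.

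The protocol also puts these participants in the population for its 3-month primary analysis while one section tells sites to stop collecting their data at 30 days. A later choice of analysis set cannot recover data that were not collected.

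**Working it through.** No figure in the plan bears directly on this point, so the check is a trace of one participant through both documents, followed by an illustration of size. The participant is eligible, has the catheter placed, has no confirmed flow, and is never dialysed through the catheter.

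**Trace under the protocol**

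1. Technical Success (3.2): can be yes, since only placement is judged.
2. Procedure Success (Appendix A): no.
3. Follow-up: 7.4.1 gives the procedure eCRF with safety events and interventions for up to 30 days; 7.5 gives the full period or until removal. Both apply to this participant.
4. ITT (10.3): included, and so in the 3-month primary analysis (10.5).
5. Within 30 days, a revision for a listed cause, or removal or abandonment with a new access, can count in the primary endpoint (3.1). Removal counts against catheter survival, and an intervention counts against patency (3.2). After day 30, if 7.4.1 prevails, nothing more is captured.

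**Trace under the SAP**

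1. Technical Success (5.3.3, ITT): can be yes.
2. mITT (4.1): excluded, because there was no first dialysis session.
3. Primary endpoint, catheter survival and patency: absent. The patency rule in 5.3.6 also counts a re-intervention only if it is dated after the first dialysis session.
4. Remaining appearances: the 1-month ITT related-AE endpoint (5.3.2) and the disposition, AE and device-deficiency summaries (6.1, 7, 6.9).

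**The 1-month window** (taking a month as 30 days, as the SAP's day 105 for 3 months plus 15 days implies)

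- Lower limit: 30 − 7 = day 23. Upper limit: 30 + 7 = day 37.
- SAP 5.3.2 scores a failure for a related AE up to day 37, non-evaluable for a listed exit before day 23, and success otherwise.
- Exit at day 30 is after day 23, so without an earlier AE the participant scores as event-free although days 31 to 37 (7 days) were not observed.

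**Illustrative size.** The documents do not give the number *k* of placements without confirmed flow. Assume *k* = 3 to 7 of 142 (about 2% to 5%), with exact binomial 95% intervals.

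- Placement only: 142/142 = 100% (97.4 to 100), whatever *k* is.
- Placement with flow, *k* = 3: 139/142 = 97.9% (94.0 to 99.6).
- Placement with flow, *k* = 7: 135/142 = 95.1% (90.1 to 98.0).
- If all *k* are never dialysed through the catheter, an mITT of 142 falls to 139 or 135.
- Primary exposure lost if 7.4.1 prevails and the catheter stays in to day 90: up to 90 − 30 = 60 days each. 60 × 3 = 180 and 60 × 7 = 420 days; 180/12,765 = 1.4% and 420/12,765 = 3.3% of planned exposure.
- Pooled primary rate: at 31.5 per 1000 days, 12,765 days give 0.0315 × 12,765 = 402.1 events. Adding one event per affected participant with 1 day of exposure each gives 405.1/12,768 = 31.73 (*k* = 3) or 409.1/12,772 = 32.03 (*k* = 7) per 1000 days. With 30 days each it gives 405.1/12,855 = 31.51 or 409.1/12,975 = 31.53.

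**The case against.** **Introduced is not placed.** Protocol 7.4.1 speaks of catheters introduced, while 7.5 and the ITT speak of catheters placed. One could read 7.4.1 as covering only catheters introduced and not successfully placed, which would be Technical failures outside the protocol ITT. The wording does not confine it to those: a catheter placed without confirmed flow has also been introduced without procedure success. What stands is that the loss of data comes from two conflicting sections and is not certain, since 7.5 might be followed.

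**A reader might infer that such a catheter fails no performance endpoint at all.** The documents do not support that in general. Under the protocol's ITT, interventions within 30 days can still count. The full absence arises only under the SAP, and only if the catheter is never used for dialysis. A catheter dialysed through later could be recorded as treated with the study device, enter the mITT and fail there; the SAP does not tie that CRF category to the Appendix A definition.

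**A reader might infer that it is reported only as a success.** It is not. SAP 6.1 reports inserted-but-never-dialysed participants as their own disposition category, SAP 7 summarises AEs on the ITT, and SAP 6.9 summarises device deficiencies.

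**A reader might infer that the primary endpoint cannot be analysed for these participants.** It can. SAP 5.2.1 ends exposure at discontinuation, so exit at day 30 shortens follow-up.

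**Placement and function are legitimately separate measures, and the investigator judges placement.** Both are true. An investigator may decline to call a no-flow placement successful, so the right word is can. That supports reporting the two measures side by side; it does not require redefining Technical Success.

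**Conclusion.** The point holds in this form. Technical Success has no flow criterion, Procedure Success has one, and 7.4.1 uses the latter to restrict data to 30 days for participants whom 7.5 keeps in the study and whom the protocol ITT includes at 3 months. Under the SAP, a placed catheter never used for dialysis drops out of the primary endpoint, catheter survival and patency but stays in the Technical Success denominator, where it can count as a success. The 30-day limit also leaves up to 7 days of the 1-month related-AE window unobserved but scored as event-free.

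The size depends on an unstated frequency. At the assumed 3 to 7 of 142, Technical Success could be overstated relative to placement with flow by 2.1 to 4.9 percentage points. The pooled primary rate moves by at most about 0.5 per 1000 days in the illustration (31.5 to 32.03), small against the margin of 5. The lost-exposure figure further assumes that 7.4.1 is followed over 7.5 and that the catheter stays in place. The main effect is on the descriptive success and early performance endpoints, and the change is worth making because it is cheap.

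**What to change.** 1. In Protocol 3.2 and SAP 5.3.3, report Procedure Success (placement with confirmed flow) beside Technical Success on the same ITT denominator.
2. Reconcile Protocol 7.4.1 with 7.5 and with the ITT in 10.3. AE and re-intervention data should be collected for placed catheters through the 3-month visit or removal, and at least to the end of the 1-month window (day 37) for everyone into whom the catheter was introduced.
3. In SAP 5.3.5 and 5.3.6, add an ITT sensitivity analysis of catheter survival and patency that counts catheters placed but never usable for dialysis as failures. The first two changes alone would leave these participants outside the mITT.

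The cost is wording in both documents, one added sensitivity analysis for two endpoints, and a few extra telephone contacts. Sites must already determine procedure success to apply 7.4.1. The reported success rates may be slightly lower.

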7.4.2 Unscheduled Follow-up

An unscheduled visit eCRF should also be completed for participants who return for additional unscheduled examination(s) pertaining to their HD vascular access. The participant will be required to complete the next scheduled follow-up visit if the unscheduled visit is out of the CIP allotted follow-up window or if the required elements of the respective follow-up were not completed as part of the unscheduled visit.

If the participant is treated by a health-care professional other than the PI for treatment related complications during the course of the follow-up period, the PI or authorized designee should request copies of the medical records and, if necessary, complete the appropriate eCRFs.

